## 8.0 Assessment of Adverse Events

### 8.1 *Definition of Adverse Events*

**Adverse Event:** An adverse event (AE) is defined as any untoward medical occurrence, including an exacerbation of a pre-existing condition, in a patient in a clinical investigation who received a pharmaceutical product. The event does not necessarily have to have a causal relationship with this treatment.

**Serious Adverse Event:** A serious adverse event (SAE) is defined as any AE which results in death, is immediately life-threatening, results in persistent or significant disability/incapacity, requires or prolongs patient hospitalization, is a congenital anomaly/birth defect, or is to be deemed serious for any other reason if it is an important medical event when based upon appropriate medical judgment which may jeopardize the patient and may require medical or surgical intervention to prevent one of the other outcomes listed in the above definitions.

**Intensity of Adverse Event:** The intensity of the AE should be judged based on the following:

1. Mild: the adverse event is temporary and easily tolerated by the subject;
2. Moderate: the adverse event causes the subject discomfort and interrupts the subject's normal activities.
3. Severe: the adverse event causes considerable interference with the subject's normal activities and may be incapacitating or life threatening including hospitalization or prolongation of hospitalization.

### 8.2 *Adverse Event Reporting*

Investigators will report serious adverse events (SAE), using standardized event, resolution and association codes. The SAE reporting period includes the entire study duration (3 months) and an additional week. All SAEs will be reported. Non-serious Adverse Events (AEs) unrelated to Apixaban treatment will not be reported.

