## 2.0 Study Objectives

### 2.1 Overall Aim and Hypothesis

The primary aim of the Eliquis Acute Stroke Safety Evaluation registry is to demonstrate the safety of early anticoagulation with apixaban following cardioembolic stroke and TIA. Safety will be established by demonstrating low rates of hemorrhage in this setting. The secondary study objective is to document the rate of recurrent cerebrovascular ischemic events. It is fully recognized that this uncontrolled registry study is not properly designed and underpowered to demonstrate a reduction in cerebrovascular ischemic events.

We hypothesize that early initiation of apixaban within the first 14 days of stroke or TIA is not associated with increased symptomatic intracranial haemorrhage.

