#### 2.2.2 Secondary Outcomes:

1. Any parenchymal haemorrhage (PH1 or PH2) on follow-up MRI scan at  $7\pm2$  days post-enrolment.
2. Recurrent TIA/Ischemic Stroke within 90 days of enrolment.
3. Systemic hemorrhagic complication rate within 90 days of enrolment.

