### 6.3 Clinical Follow-up Assessments

All patients will be followed for 90 days. This is the standard post-stroke assessment period (the majority of neurological and functional recovery occurs within this time frame). Patients will be assessed clinically at follow-up visits performed on Day 7 ( $\pm 2$  days), and Day 90 ( $\pm 30$  days) by a study team member (i.e. co-investigator, study coordinator). At each visit, vital signs will be noted, a comprehensive neurologic examination will be performed and mRS, NIHSS and MoCA

assessments will be conducted with the patient. Patients will be interviewed in detail to identify and ascertain any recurrent vascular event suggestive of a stroke or TIA. Work-up to determine the underlying etiology of stroke will be reviewed and any change in management plan will be recorded.

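### The protocol describes no causality-independent capture of non-serious systemic bleeds, so the 90-day systemic bleeding rate can be biased downward

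*Protocol*

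**What the plan says.** Section 2.2.2 lists as the third secondary outcome "Systemic hemorrhagic complication rate within 90 days of enrolment". The term is not defined, and nothing restricts it to serious or drug-related bleeds. Section 2.1 ties the safety conclusion to bleeding counts: "Safety will be established by demonstrating low rates of hemorrhage in this setting".

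Section 8.1 defines an adverse event without a causality condition: "The event does not necessarily have to have a causal relationship with this treatment". Section 8.2 then treats events by seriousness. For serious events, "All SAEs will be reported", and "The SAE reporting period includes the entire study duration (3 months) and an additional week". For the rest, "Non-serious Adverse Events (AEs) unrelated to Apixaban treatment will not be reported".

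For the Day 7 and Day 90 visits, section 6.3 lists vital signs, a neurological examination, mRS, NIHSS and MoCA. It then says "Patients will be interviewed in detail to identify and ascertain any recurrent vascular event suggestive of a stroke or TIA", and finally "Work-up to determine the underlying etiology of stroke will be reviewed and any change in management plan will be recorded". Bleeding is not mentioned.

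Section 9.0 provides central adjudication for brain imaging only. The protocol gives no criteria for relatedness and no adjudication of systemic bleeds.

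**The concern.** An outcome count should not depend on whether someone believes the drug caused the event. Here the outcome has no causality limit, but the one reporting channel that the protocol describes for non-serious events does. The judgement is made by investigators who know the treatment, because everyone receives apixaban (section 3.0: open label, single arm).

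Three features make this worth settling before data collection:

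- The possible error has one direction. Dropping events can only lower the bleeding rate, and a low rate is the result that section 2.1 counts as evidence of safety.
- There is no comparator arm in which a similar loss would occur and partly cancel.
- The loss happens at collection. No later analysis plan can restore events that sites were told not to report. Sections 1.1 and 7.0 say the results will inform a larger trial, so a rate that is too low would carry forward.

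**Working it through.** **Step 1: which bleeds have a described route into the data.**

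| Systemic bleed | Route described | Depends on a causality opinion? |
|---|---|---|
| Serious, any attribution | SAE reporting, 3 months plus a week (8.2) | No |
| Non-serious, judged related | AE reporting, by implication of 8.2 | Yes, but kept |
| Non-serious, judged unrelated | None stated; excluded from AE reporting (8.2) | Yes, and can be lost |

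The interview in 6.3 names stroke and TIA, so it does not expressly cover the third row. The record of management changes may reveal a bleed that altered treatment, but it is not a bleeding enquiry.

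**Step 2: size of the possible loss.** The protocol gives no systemic bleeding rate, so there is no figure to reproduce. The only documented input is N = 50 (section 7.0, a convenience sample). The other inputs are assumptions:

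- p = true 90-day systemic bleeding rate: 4%, 10% or 20%
- s = share of bleeds that are serious: 0.2 to 0.5
- u = share of non-serious bleeds judged unrelated: 0, or 0.1 to 0.5

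Formulas:

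- lost share = (1 − s) × u
- reported rate = p × [s + (1 − s)(1 − u)] = p × (1 − lost share)
- chance of losing at least one bleed = 1 − [1 − p(1 − s)u]^50

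Lost share:

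- u = 0: 0%, whatever s is
- s = 0.5, u = 0.1: 0.5 × 0.1 = 5%
- s = 0.2, u = 0.5: 0.8 × 0.5 = 40%

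Results for u from 0.1 to 0.5 and s from 0.2 to 0.5:

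| Assumed p | Expected true bleeds in 50 | Expected reported | Reported rate | Chance of losing at least one |
|---|---|---|---|---|
| 4% | 2.0 | 1.2 to 1.9 | 2.4% to 3.8% | 10% to 55% |
| 10% | 5.0 | 3.0 to 4.75 | 6.0% to 9.5% | 22% to 87% |
| 20% | 10.0 | 6.0 to 9.5 | 12.0% to 19.0% | 40% to 98% |

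With u = 0 the reported rate equals p in every row. In 50 patients, each patient whose only bleed is lost lowers the rate by 1/50 = 2 percentage points.

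**Step 3: which endpoints are touched.** The primary endpoint (PH2 with an NIHSS worsening of at least 4 points) and the major secondary endpoint (PH1 or PH2 on MRI) are established from imaging, with NIHSS for the former. They do not pass through the rule in section 8.2.

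**The case against.** The strongest reply is that section 8.2 governs adverse-event reporting, not outcome ascertainment. Systemic haemorrhage is a listed outcome in its own right, and section 6.1 shows that a case report form exists. That form is not available here, and it may well have a bleeding field. This stands as a limit: separate capture is not excluded. It does not remove the point, because the protocol does not describe such capture and its stated rule makes no exception for outcome bleeds.

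Second, everyone in the study takes an anticoagulant, so a bleed may seldom be judged unrelated, and the loss could then be near zero. Also, the outcome term is undefined. If it means clinically significant bleeding, many such events would be serious and therefore kept. Both arguments bear on size, and they are why the range must start at 0%.

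Third, this is one of the other secondary endpoints, with no test attached, in a small sample meant for planning. That is fair and limits the weight of the point.

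A reader might also infer two stronger things that the text does not support. One is that the visits ask about nothing but stroke or TIA. Section 6.3 names only those, but it is not worded as exclusive. The other is that recurrent TIA, also an outcome, suffers the same loss. The interview looks for TIA in detail at both visits, and nothing makes that enquiry depend on relatedness to apixaban.

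**Conclusion.** The point holds in limited form. Sections 2.2.2, 6.3 and 8.2 do not fit together: the outcome has no causality limit, and no causality-independent capture is described for non-serious systemic bleeds. The 90-day systemic bleeding rate can therefore be biased downward.

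It would go too far to say that the whole endpoint is filtered by causality, or that it will undercount. Serious bleeds are reported whatever their cause, and only bleeds that are both non-serious and judged unrelated are at risk. The direction follows from the rule. The size does not follow from anything in the document, and the range of 0% to about 40% rests entirely on the assumed values of s and u. This is a worthwhile correction to a secondary safety outcome. It does not threaten the primary result.

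**What to change.** - In section 8.2, add that all systemic bleeding events are recorded on the case report form regardless of seriousness or relationship to apixaban.
- In section 6.3, add a bleeding question to the Day 7 and Day 90 interviews.
- In section 2.2.2, define which bleeds count as a systemic haemorrhagic complication. State that every bleed meeting the definition enters the 90-day rate, with relatedness shown only as a descriptor.

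With every bleed recorded whatever its attribution, u has no effect and the loss through this rule is zero for any bleed that comes to light. If the case report form already captures bleeds separately, a clarifying sentence in section 8.2 is enough to remove the conflict with the reporting rule.

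The cost is a few sentences and one form item at visits already planned, plus some extra minor-bleed entries. No treatment or visit schedule changes.

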## 9.0 Central Imaging Adjudication and Analysis

Dicom CT and MRI data will be transferred to the Stroke Imaging Laboratory at the University of Alberta for post-processing and analysis. All image assessments will be performed using software developed specifically for CT brain image analysis (Quantomo software package, Cybertrial Inc, Calgary, AB). The extent of any objective acute and chronic ischemic changes on all CT scans will be assessed using Alberta Stroke Program Early CT Scores (ASPECTS). The extent of subacute ischemic changes will also be assessed using the day 1 MRI (Diffusion-Weighted Imaging sequences). Infarct volumes will be measured objectively using planimetric techniques. The extent of periventricular leukoarosis will also be measured using planimetric techniques and an intensity threshold algorithm included in the Quantomo software package.

[figure not shown]
All cases of hemorrhagic transformation seen on post-dabigatran treatment scans will be graded using the ECASS (European Cooperative Acute Stroke Study) hemorrhage classification scheme:

1. PH2 - parenchymal hemorrhage as a blood clot in more than 30% of the infarcted area with substantial space-occupying effect.
2. PH1 - parenchymal hemorrhage as blood clots in 30% or less of the infarcted area with some slight space-occupying effect.
3. HT2 - hemorrhagic transformation 2 - confluent petechiae within the infarcted area but no space-occupying effect.
4. HT1 - hemorrhagic transformation 1 – small petechiae along the margins of the infarct.
5. R - remote ICH, i.e. not topographically related to the infarct (most often in the contralateral hemisphere).

A symptomatic ICH (primary endpoint) will be defined as PH2, associated with an NIHSS deterioration of  $\geq 4$  points. The primary endpoint will be assessed using the day 7 MRI scan and any additional scans performed within 30 days of apixaban initiation.

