### 2.2 Outcome Variables

#### 2.2.1 Primary Outcome:

Symptomatic Hemorrhagic Transformation Rate (PH2) associated with clinical deterioration, defined as worsening of NIHSS score of 4 or more points within 30 days of initiating anticoagulant therapy.

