## 4.0 Enrolment Criteria

### 4.1 Inclusion Criteria

1. Male or female patients
2. Must be  $\geq 18$  years of age.
3. Diagnosis of minor ischemic stroke, or Transient Ischemic Attack (TIA, defined as acute focal neurological deficits, with complete resolution of symptoms within 24 h of onset). In cases where onset time cannot be established, it will be considered to be the time when patient was last known to be well.
4. CT scan or MRI, with findings consistent with an ischemic etiology of symptoms.
5. Atrial Fibrillation (AF, paroxysmal or persistent), confirmed with ECG/Holter monitor, or by history (clinical documentation of previous AF must be provided).
6. Patients prescribed apixaban by their treating physician following their stroke/TIA.
7. Ability to obtain consent from patient or legally authorized representative.

**Note:** The decision to treat with apixaban and the timing of the first dose will be determined by the attending physician, independent of the registry. Consent to participate in the registry will be obtained only after the treating physician has made the decision to initiate apixaban therapy within 14 days of stroke/TIA.

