## 7.0 Statistics

The primary outcome will be tested with a single sample t-test. The null hypothesis is that the frequency of symptomatic hemorrhagic transformation is <2%. A convenience sample of 50 patients is planned initially. This will provide initial safety and feasibility data that can be used to plan future definitive studies as required. The primary efficacy analysis will be on an intention-to-treat basis.

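### The primary haemorrhage grade needs an infarct, but eligibility does not clearly require one, so infarct-free patients can enter the 50 and lower the single rate compared with 2%

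*Protocol*

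**What the plan says.** **Endpoint.** Protocol section 2.2.1 names the primary outcome "Symptomatic Hemorrhagic Transformation Rate (PH2) associated with clinical deterioration", with deterioration set at 4 or more NIHSS points within 30 days of starting anticoagulation. Section 9.0 repeats it: "A symptomatic ICH (primary endpoint) will be defined as PH2, associated with an NIHSS deterioration of" 4 points or more. The grade itself is "PH2 - parenchymal hemorrhage as a blood clot in more than 30% of the infarcted area with substantial space-occupying effect". PH1 is the same kind of bleed in 30% or less of the infarcted area, and PH1 or PH2 on the day 7 MRI is the major secondary outcome. Bleeding elsewhere has its own grade, "R - remote ICH, i.e. not topographically related to the infarct (most often in the contralateral hemisphere"), which belongs to neither outcome.

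**Eligibility.** Section 4.1, criterion 3 asks for "Diagnosis of minor ischemic stroke, or Transient Ischemic Attack (TIA, defined as acute focal neurological deficits, with complete resolution of symptoms within 24 h of" their start). Criterion 4 asks for "CT scan or MRI, with findings consistent with an ischemic etiology of symptoms". Section 6.1 names non-contrast CT as the initial screen. The diffusion-weighted MRI is done within 24 hours of recruitment (section 6.2.1).

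**Analysis.** Section 7.0 states: "A convenience sample of 50 patients is planned initially", and "The null hypothesis is that the frequency of symptomatic hemorrhagic transformation is <2"%. It compares one frequency with 2% and makes no reference to infarct status. Its only analysis-set statement is intention-to-treat, worded for efficacy.

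**Aim.** Section 2.1 covers stroke and TIA together, takes low haemorrhage rates as the evidence of safety, and words the hypothesis in terms of symptomatic intracranial haemorrhage.

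**The concern.** The grade that defines the event is a fraction of the infarcted area. A patient with no infarcted area has nothing to which the grade can apply. If such patients are enrolled, they add to the denominator and cannot add to the numerator unless they infarct later. The rate then falls as their share rises, whatever the drug does, and it falls in the direction that the study would read as safe.

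There is a second gap. If an infarct-free patient has a symptomatic intracranial bleed, the bleed is not PH2. The hypothesis in section 2.1 would cover it and the primary endpoint would not.

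Two uses of the result are at stake: the safety statement itself, and the planning of the randomised trial in section 1.1. That section says the true rate of symptomatic haemorrhagic transformation is not known, and it describes treatment timing as governed by infarct extent. A rate averaged over patients with and without infarcts does not answer that question for patients with infarcts.

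**Working it through.** **The plan's own figures.** There is no derivation to reproduce. The 50 is a convenience sample, and 2% is stated without a source, error rate or alternative. One event in 50 is 1/50 = 2.0%, exactly the reference value.

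**Inputs.** From the protocol: N = 50 and the reference of 2% (section 7.0), and PH2 tied to the infarcted area (section 9.0). Assumed, because the protocol gives neither: the share *f* of enrolled patients without an infarct, and a 4% event rate among patients with one.

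**Formulas.**
- Pooled rate = (1 − *f*) × rate in infarct patients, if no infarct-free patient infarcts later.
- Patients at risk: *m* = 50 × (1 − *f*).
- Chance of zero events = 0.96^*m*.
- Two-sided 95% exact upper limit after zero events = 1 − 0.025^(1/*m*).

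**Results.**

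| Assumed *f* | At risk *m* | Pooled rate if infarct rate is 4% | Chance of zero events | One event as a share of *m* | Upper limit after zero events, on *m* |
|---|---|---|---|---|---|
| 0% | 50 | 4.0% | 0.130 | 2.0% | 7.1% |
| 20% | 40 | 3.2% | 0.195 | 2.5% | 8.8% |
| 40% | 30 | 2.4% | 0.294 | 3.3% | 11.6% |
| 50% | 25 | 2.0% | 0.360 | 4.0% | 13.7% |

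At *f* = 25% the pooled rate is 4% × 0.75 = 3.0%.

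Read the other way, a pooled 2% corresponds to 2%/(1 − *f*) in infarct patients: 2.5% at *f* = 20%, 3.3% at 40% and 4.0% at 50%.

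The direction holds for every *f* above zero. At *f* = 0 there is no effect.

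**The case against.** Four stronger readings are tempting, and the document supports none of them.

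- **Infarct-free TIA patients are in the sample.** The protocol never says so. Criterion 4 can be read as asking for a positive ischaemic finding, which would keep many of them out. A TIA defined by symptom duration can also leave an infarct. What stands is that the criterion can equally be applied to a TIA with no visible lesion, and nothing in the text settles it.
- **The pooled rate is biased.** The declared target is stroke and TIA, and the later trial is described for both. For that population an all-enrolled rate is legitimate. It misleads only when read as the transformation risk of patients with an infarct, or as the rate of all symptomatic intracranial bleeding.
- **The primary analysis should move to patients with an infarct on baseline MRI.** That is a debatable trade. It leaves the evaluable number unknown until after recruitment, and it would drop a PH2 in a patient who infarcts after enrolment, although section 9.0 counts any scan within 30 days.
- **Case mix drives the rate as much as the drug does.** Nothing in the document supports a statement of that strength.

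It is also fair to say that imprecision dominates. The zero-event limit of 7.1% on all 50 already exceeds 2%. Moving from 4% to 3% changes the expected count only from 2.0 to 1.5 events. Analysis sets and subgroup reporting may sit in a statistical analysis plan that is not shown. Remote bleeds are graded, and all serious adverse events are reported, so the bleeding data would exist.

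What remains is in the protocol itself: an endpoint that requires an infarct, an entry rule that does not clearly require one, one frequency set against 2%, and a hypothesis broader than the endpoint.

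**Conclusion.** The point holds as a gap between endpoint and population. It is not a demonstrated dilution. Patients without an infarct can enter the 50, cannot have the primary or major secondary event unless they infarct later, and lower the single rate compared with 2%. A symptomatic bleed in such a patient would be missed by the primary endpoint.

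The size rests on two assumptions, the infarct-free share and the 4% rate. Under them the pooled rate is 3.0% at a 25% share and 2.0% at a 50% share. The zero-event upper limit does not depend on the 4%: it is 7.1% if all 50 are at risk and 13.7% if 25 are. If criterion 4 is meant to require a visible infarct, and is applied that way, the effect largely disappears, but the protocol has to say so.

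The change is worth making because the data are already planned and the remedy does not disturb the all-enrolled rate.

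**What to change.** In sections 2.2, 7.0 and 9.0:

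1. Keep the all-enrolled rate for the stroke and TIA target.
2. Prespecify beside it the PH2 rate (with the NIHSS condition) and the PH1/PH2 rate, each with an exact interval, among patients with an acute infarct on the MRI Study 1 diffusion images, or on the qualifying CT if no MRI was done. State how many were classified by CT.
3. Report any symptomatic intracranial haemorrhage, including grade R, for all patients and separately for those without an infarct. A bleed after a later infarct is then still counted.
4. Base statements about haemorrhagic transformation risk, and the planning of the later trial, on the infarct-group rate.

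In section 4.1, state whether criterion 4 requires a visible infarct.

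**Cost.** No new data are needed: diffusion imaging is planned for every patient, a contraindication to MRI is an exclusion, and infarct volume is already measured. The price is a smaller denominator, unknown in advance, and a wider interval for the infarct-group rate.

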## 10.0 Funding Source

This investigator-initiated study is funded by the Alliance. The funding will be used for MR imaging.

